9.1 Informed Consent/Assent Process (in Case of a Minor or Others Unable to Consent for Themselves)	14
10 Literature References	15
Supplements / Appendices	16
Standard Operating Procedure (SOP) Summary of Laboratory Work	16
Standard Operating Procedures Summary (SOP) for Data Collection and Field Work	17
Informed Consent Script to Be Read in Population-Based Field Surveys	18

List of Abbreviations

Alb	Albendazole
APOC	African Programme for Onchocerciasis Control
CFR	Code of Federal Regulations
CRF	Case Report Form
DEC	Diethylcarbamazine
DMID	Division of Microbiology and Infectious Diseases, NIAID, NIH
DSMB	Data Safety Monitoring Board
ELF	Elimination of Lymphatic Filariasis
FWA	Federal-Wide Assurance
GCP	Good Clinical Practice
GPELF	Global Programme to Eliminate Lymphatic Filariasis
IATA	International Air Transport Association
ICH	International Conference on Harmonisation
ICIDR	International Collaboration for Infectious Disease Research
ICT	Immunochromatography Test
IntTrans	Interruption of transmission
IRB	Institutional Review Board
IVER	Ivermectin
LF	Lymphatic Filariasis
MDA	Mass Drug Administration
MF	Microfilaria(e)
OCP	Onchocerciasis Control Programme
OHRP	Office for Human Research Protection
ONCHO	Onchocerciasis
OSHA	Occupational Safety and Health Administration
PELF	Program to Eliminate Lymphatic Filariasis
PI	Principal Investigator
SAE	Severe adverse events
SOP	Standard Operating Procedure
STH	Soil transmitted helminths
WHO	World Health Organization

Protocol Summary

Title: Optimization of Mass Drug Administration with existing drug regimens for Lymphatic Filariasis and Onchocerciasis

Population: Approximately 6,400 people will participate per year. The study population will include females and males over 5 years of age who live in filariasis endemic areas. Subject selection will not be based on health status.

Number of Sites: Two sites in Indonesia (in separate *B. timori* and *W. bancrofti* endemic areas)

Study Duration: 4 years

Subject Duration: Participants will be studied only once in cross-sectional surveys. Some subjects may be included in more than one annual population survey, but this is not a longitudinal study.

Objectives: To evaluate different mass drug administration (MDA) regimens for lymphatic filariasis and its impact on soil transmitted helminthes. MDA is administered by others (e.g., Ministry of Health) and may enhance efforts to control and eliminate these important neglected tropical diseases.

1. We will compare the relative impact and cost effectiveness of annual vs. twice yearly mass drug administration (MDA) for elimination of lymphatic filariasis (LF).
2. We will also study the impact of annual vs. semiannual MDA on soil transmitted helminth (STH) infection in these populations.

Remarks on the project structure: The Project “Optimization of Mass Drug Administration with existing drug regimens for Lymphatic Filariasis and Onchocerciasis” has 3 major Objectives (Objective 1-Community MDA Trials, Objective 2-Randomized Clinical Trials and Objective 3-Pilot Flubendazole Studies). Objective 1 will be conducted in 4 countries in Africa and 2 countries in the Asia. Although the overall objectives are similar, there are country-specific modifications. This protocol was developed for Indonesia.

2 BACKGROUND INFORMATION AND SCIENTIFIC RATIONALE

2.1 Background Information

Lymphatic filariasis (LF) is a deforming and disabling infectious disease that causes elephantiasis and genital deformity (especially hydroceles). The infection affects some 120 million people in 81 countries in tropical and subtropical regions with well over 1 billion people at risk of acquiring the disease [1]. LF is caused by *Wuchereria bancrofti* and *Brugia* spp. (*B. malayi* and *B. timori*), nematode parasites that are transmitted by mosquitoes. The World Health Organization (WHO) developed a plan for LF elimination that is based on using novel approaches to rapidly map endemic areas and 4 to 6 annual rounds of mass drug administration (MDA) with antifilarial medications [2, 3]. A recent report from WHO reported that more than 1.9 billion doses of MDA were distributed between 2000 and 2007 [4]. Thus, the Global Programme to Eliminate Lymphatic Filariasis (GPELF) is the largest infectious disease intervention program attempted to date based on MDA. MDA has worked better in some areas than others. A recent publication reviewed challenges faced by GPELF [5]. The limited macrofilaricidal activity of current MDA regimens (especially Ivermectin/Albendazole) that necessitate repeated annual rounds of MDA, and the difficulty of achieving high compliance rates for MDA over a period of years. ***It is clear that new dosing schedules for MDA have the potential to greatly improve the number of countries that will successfully eliminate LF by the WHO target date of 2020.***

Drugs used for LF MDA are also active against soil transmitted helminths (STH, e.g., *Ascaris*, Hookworm, and *Trichuris*). The estimated numbers of infected individuals (in millions) for *Ascaris*, hookworm and *Trichuris* range from 807-1227, 576-740, and 604-795 respectively [6]. De-worming campaigns using anthelmintics usually target special groups of the population, such as schoolchildren, and have limited impact on the transmission. Treatment of the total population and semiannual treatments may reduce re-infection considerably and will most likely lead to reduced infection densities and infection prevalences. ***Suppression of STH is an important ancillary benefit of MDA programs for filarial infections [2].***

2.2 Rationale

This study is based on the assumption that currently used MDA regimens and schedules are not optimal for achieving elimination of LF. These regimens (either annual Alb 400 mg plus DEC 6 mg/kg or Alb 400 mg plus Iver 200 µg/kg for LF) were developed more than 10 years ago [3, 7].

WHO (WHA 50.29) has targeted LF for global elimination by the year 2020. GPELF recommends 4 to 6 years of annual MDA [2]. However, the likelihood of this strategy to succeed depends on a number of factors [5]. While some national MDA programs have succeeded, others

are struggling to sustain MDA with high coverage rates for 5 to 7 years according to WHO guidelines, and others have not completed mapping or initiated MDA. Annual DEC/Alb may be sufficient to eliminate LF in endemic areas with low to moderate endemicity when high MDA coverage (at least 75%) can be sustained for 5 or more years. However, in a few countries in South East Asia the endemicity is high in some areas and annual DEC/Alb may not be optimal. In addition, the Iver/Alb regimen used for LF in Africa is less active against adult worms than DEC/Alb, and annual Iver/Alb may not be sufficient to eliminate LF in Africa. We assume that more effective and efficient MDA regimens might tip the balance toward LF elimination in areas that are failing or at risk of failing to reach elimination targets with current regimens. Therefore, the goal of Objective 1 is to compare intensive (twice per year, 2X) MDA with conventional annual MDA (1X) to determine whether improved efficacy of the 2X regimens justifies increased resources required for this more intensive treatment. These trials are based on two major *assumptions*:

A. We assume that 2X MDA regimens will reduce the time needed to reach LF elimination targets. 2X MDA should shorten the time it takes to interrupt transmission (preventing infections that would otherwise have to be treated in later years); depending on the drug combination used and parasite species targeted, 2X treatment should also lead to faster clearance of adult worms. Current MDA treatment strategies are based on interrupting transmission for the reproductive life span of the adult worms (estimated to 5-7 years for species that cause LF). However, these durations may be overly conservative, because they do not factor in the partial macrofilaricidal activity of repeated rounds of treatment. Accelerated MDA programs may improve compliance and reduce costs for social mobilization and training expenses for health personnel. These factors may reduce the time required to reach elimination targets. In addition, more intensive LF elimination programs may be more attractive for public health officials to undertake than programs that require 6 years or longer.

B. Suppression of STH is an important ancillary benefit of MDA programs for LF [2]. We assume that 2X MDA will be more effective for this purpose than annual MDA. The impact of MDA on STH varies for different parasite species and drug regimens [8, 9]. For example, *Ascaris* and hookworm are more susceptible to Albendazole than *Trichuris*. Persistence of *Ascaris* eggs in soil limits the ability of MDA to reduce *Ascaris* transmission.

2.3 Potential Risks and Benefits / Potential Risks

2.3.1 Potential Risks

This research includes risks associated with collection of blood by finger prick

Likely	Collection of blood causes minor pain
Less Likely	Collection of blood can cause a bruise, bleeding or infection at the collection site. To minimize risks, sterile disposable lancets will be used for blood collection. Blood will be collected by experienced technicians after disinfecting the skin with alcohol. Subjects will be instructed to apply pressure to finger prick sites to minimize bleeding and hematoma formation. The amount of blood being collected (less than 1 ml) is not enough to cause anemia.

There are no risks associated with collection of stool samples.

Long range risks: None

- *Rationale for the necessity of such risks:* **Blood is required for diagnosis of filarial infections. Procedures in this project meet the definition of “minimal risk”.**
- *Alternative data gathering procedures that have been considered or will be considered:* **None. Blood is needed for diagnosing filarial infections which are the subject of this project.**
- *Why the value of the information to be gained outweighs the risks involved.* **The potential benefits to individuals, society and science are considerable. The risks are minimal.**

2.3.2 Potential Benefits

- To subjects:
The study will screen participants for filarial infections and refer infected subjects for free treatment at their local government health center.
- To society:
Participation will provide information on the impact of MDA on filarial and STH infections that affect the public health in the community.

3 OBJECTIVES

To conduct population-based field studies to determine the relative cost and efficacy of annual vs. semiannual MDA for elimination of lymphatic filariasis.

1. We will test the hypothesis that twice annual MDA is superior to annual MDA for eliminating lymphatic filariasis.
2. We will test the hypothesis that twice annual MDA is superior to annual MDA for controlling soil transmitted helminth infections.

4 STUDY DESIGN

(Please read this section together with Section 5, “Study Population”)

The project is comprised of repeated annual cross-sectional surveys in sentinel communities before and after initiation of MDA for LF. MDA (standard regimens recommended by WHO) will be provided by government health officials. Data collection will include demographic data, history of lymphedema, scrotal swelling (hydrocele), acute filarial fever or adenolymphangitis, prior treatment for LF. Blood samples (400 µL per person) will be collected from systematically sampled households. Blood will be tested for filarial antigenemia with the Binax Now Filariasis Card Test and Alere Filariasis Strip Test (which detects *Wuchereria bancrofti* antigen in blood, manufactured by Alere, Portland ME, USA). Blood from persons with positive filarial antigen tests will also be tested for microfilaremia (see Section 6 below for methods). The *Brugia* Rapid (BmR1) test will be used to detect antibodies to *Brugia* parasites antibodies in serum or blood samples. Stool examinations will also be performed for diagnosis of STH infections. **Note not all test will be performed on blood and stool samples.**

Safety oversight: Study personnel will monitor subjects for adverse events related to blood collection. No medical monitor or DSMB is needed for this minimal risk, non-intervention study.

Time to collect specimens: Most participants in the community will only be studied once (demographic data, blood, and stool samples). Thus, the **duration** of subject participation will be one day.

Parameters and criteria for assessing the impact of MDA:

Blood tests for *Wuchereria bancrofti* infection, Binax Now Filariasis Card Test and Alere Filariasis Strip Test (with MF testing of antigen positive subjects): We are using these tests as a measure of LF endemicity. The rapid tests detect antigen released from living adult filarial worms potentially capable of resuming MF production in the future. The antigen tests are much more sensitive for *W. bancrofti* infection than tests for microfilaremia. However, antigen tests may

remain positive years after treatment has cleared microfilaremia. The antigen tests will be performed in individual residents over 5 years of age. This will be done by sampling approximately 100 randomly selected households per sentinel site (village) to produce N of 400. There will be 4 sentinel sites for each treatment zone (annual vs twice annual MDA). The target number of samples per village is close to the minimum sample size of 335 needed to show that the rate of antigenemia (card test) positivity is less than 2% (with 95% confidence and 80% power). In post-MDA populations, this corresponds to a MF rate of less than 0.5%, which is an LF elimination target. We expect to collect 4 to 5 blood samples per household. Subjects with positive card tests will be tested for microfilaremia with 60 µl night blood thick smears. Our decision to detect MF by thick smears of finger prick blood rather than membrane filtration of venous blood is because thick smears are recommended for LF elimination program guidelines. In addition, our prior studies in Egypt have shown that L3 production by *Culex* mosquitoes that feed on MF carriers with negative thick smears is negligible. The justification for collecting blood at night for MF testing is that microfilariae of *W. bancrofti* and *B. timori* in Indonesia are nocturnally periodic with highest counts in peripheral blood between 9 p.m. and 2 a.m.

Blood tests for *Brugia timori* infection *B. timori* infections will be detected by two methods, namely microscopic examination and the BrugiaRapid Test (BmR1 antibody) Cassette (Cellabs, Malaysia). Microscopic examination of thick blood smears prepared with 60 µl of blood collected between the hours of 9 p.m. and 2 a.m. The Brugia Rapid test is a rapid diagnostic test kit for detecting antibodies to filarial parasites using serum or whole blood.

Blood samples will be collected from randomly selected households per sentinel site (village) to produce N of 400. There will be 4 sentinel sites for each treatment zone (annual vs twice annual MDA). This sample size number exceeds the minimum target sample size of 335 needed to show that the MF rate is less than 2% (with 95% confidence and 80% power, assuming an actual rate of 0.5%, which is an LF elimination target). We expect to collect 4 to 5 samples per household.

Stool examination for infection with soil transmitted helminths. We will examine stool samples of the study population mentioned above for the presence and the density of STH eggs. We will use the FLOTAC method to examine a single stool sample from each subject [10]. This quantitative method has an excellent sensitivity and will provide relatively accurate data on both prevalence and density of infection. We will use community egg loads as the primary endpoint for assessing the impact of MDA on STH infections, because this combines both prevalence and density of infection.

Hypotheses, outcomes, and methods for statistical testing are provided in Section 7, Analysis plan.

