5 STUDY POPULATIONS

Description of human subject involvement in research:

We will perform repeated annual cross-sectional surveys in study communities.

Eligibility: This project will study people who live in communities that are endemic (or that were endemic at the beginning of the study) for LF. The endemicity rate (MF rate) at baseline should be at least 10% and study areas should have limited or no prior experience with MDA for LF.

Gender, minority and child inclusion: Males and females will be included in population-based village studies without regard to race, religion, or ethnic group. There is no reason to exclude pregnant women and older children from population-based studies. Exclusion of children less than 6 years of age from community studies is justified because prevalence rates for filariasis tend to be very low in young children and because of difficulties associated with collecting clinical specimens from this population.

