7.2 Sample Size Considerations

Except as otherwise noted, all sample sizes in this protocol were calculated using a binomial power calculator (using alpha = .05, two-tailed tests, and power = .80). These sample sizes were chosen to provide confidence that measured prevalence rates will be below specified limits based on assumptions regarding true prevalence rates. The sample size analysis considered various contingencies to assess robustness of the sample size estimates (see Appendix).

Note: Sample size considerations for community surveys for demonstrating that prevalence rates are below pre-defined targets for antigenemia, microfilaremia, antifilarial antibody and STH infections are provided in Section 4, above, and this is not repeated here.

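### The 80% power claimed for showing antigenemia below 2% with 335 people per village names no true antigenemia rate, and 335 does not reach 80% even at 0.5%, the only true rate in the documents

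*Combined protocol and SAP*

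**What the plan says.** Section 4 of the combined protocol and SAP sizes the antigen survey in each village by "sampling approximately 100 randomly selected households per sentinel site (village) to produce N of 400". It describes this as near a "minimum sample size of 335 needed to show that the rate of antigenemia (card test) positivity is less than 2% (with 95% confidence and 80%", where the last figure is the power. The next sentence links the limit to microfilaremia: "In post-MDA populations, this corresponds to a MF rate of less than 0.5%, which is an LF elimination target". No true antigenemia rate is given.

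The B. timori paragraph of Section 4 uses the same number for a different marker. There 335 is the minimum "needed to show that the MF rate is less than 2% (with 95% confidence and 80% power, assuming an actual rate of 0.5"%.

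Section 7.2 says that sample sizes use a two-tailed alpha of .05 and power of .80, and that they are "based on assumptions regarding true prevalence rates". For the prevalence targets it sends the reader back to Section 4. It also cites an appendix for robustness, but the appendices named in the contents list are two SOP summaries and a consent script. Section 7.4 names antigenemia below 2% and microfilaremia below 0.5% as the control targets.

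**The concern.** A power figure for showing that a rate lies below a limit has no value until the true rate is fixed: the nearer the truth is to the limit, the lower the power. The antigenemia statement fixes none. The natural place to look is the parallel B. timori statement, but its 0.5% is a microfilaremia rate, and the protocol does not treat the markers as interchangeable. Section 4 calls the antigen tests much more sensitive than tests for microfilaremia, and says they may "remain positive years after treatment has cleared microfilaremia". Section 5 adds that "The endemicity rate (MF rate) at baseline should be at least 10"%. After treatment, antigenemia above 0.5% is therefore plausible, though the documents give no expected value.

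What is at stake is how the village surveys are read. Section 4 presents each one as having an 80% chance of demonstrating a named control target. If the chance is lower, a result that does not show antigenemia below 2% says less about the village than the stated power suggests.

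**Working it through.** **Inputs.** Limit 2%, minimum n of 335 and planned n of 400 per village (Section 4). Alpha .05, two-tailed, and power .80 (Section 7.2). Because the 95% confidence of Section 4 could be read as one-sided, both versions are shown. The true rate of 0.5% is borrowed from the B. timori paragraph; 1.0% and 1.5% are my assumptions. People are treated as independent. Section 4 expects 4 to 5 samples per household and states no design effect; clustering would generally lower power further.

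**Step 1. Reproducing 335.** Test of 2% against 0.5% at 80% power, normal formula:

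n = [(z_α√(0.02×0.98) + z_β√(0.005×0.995)) / 0.015]²

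- One-sided: [(1.645×0.1400 + 0.842×0.0705)/0.015]² = 372.9, so 373.
- Two-tailed: [(1.960×0.1400 + 0.842×0.0705)/0.015]² = 495.1, so 496.
- Exact binomial: 386 at one-sided .05, and 436 at .025 per tail.

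None of these is 335. Two other calculations do return it:

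- Hypotheses reversed (null 0.5%, alternative 2%, one-sided 5%, reject at 5 or more positives). The type I error is 2.8% and the power is 80.07% at n = 335, against 79.9% at 334.
- A precision formula with no power term: 1.96²×0.02×0.98/0.015² = 334.6.

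Neither gives 80% power to show that a rate is below 2%. The documents do not say which calculation was used.

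**Step 2. Exact decision rule.** Conclude below 2% if positives ≤ c, where c is the largest count with P(X ≤ c | n, 2%) ≤ alpha.

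- n = 335: P(X ≤ 1) = .009, P(X ≤ 2) = .036, P(X ≤ 3) = .097. So c = 2 at .05 and c = 1 at .025.
- n = 400: P(X ≤ 2) = .013, P(X ≤ 3) = .041, P(X ≤ 4) = .097. So c = 3 at .05 and c = 2 at .025.

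**Step 3. Power = P(X ≤ c | n, true rate).** For example, at n = 335 and 0.5%: .187 + .314 + .264 = .764 (rounded terms sum to .765). At n = 400 and 0.5%: .135 + .271 + .271 + .181 = .858.

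| n and test | c | 0.5% | 1.0% | 1.5% | Largest true rate with 80% power |
|---|---|---|---|---|---|
| 335, one-sided .05 | 2 | 76% | 35% | 12% | 0.46% |
| 335, two-tailed .05 | 1 | 50% | 15% | 4% | 0.25% |
| 400, one-sided .05 | 3 | 86% | 43% | 15% | 0.57% |
| 400, two-tailed .05 | 2 | 68% | 24% | 6% | 0.38% |

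**Step 4. Exact minimum n at a true 0.5%.** Power first reaches 80% at 386 (one-sided .05) and at 436 (.025 per tail). Exact power moves in a saw-tooth, and the .025 version stays above 80% only from 509 on.

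**Step 5. Treatment zone, 4×400 = 1,600 people, one-sided .05.** c = 22; power is 94% at a true 1.0% and 39% at 1.5%. With an assumed design effect of 1.5, the effective n is 1,600/1.5 = 1,067 and c = 13; power is 81% and 27%.

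**The case against.** The strongest reply is that little depends on this figure. Section 7.4 tests the primary hypothesis with a mixed model on regimen, year and their interaction. The 2% level enters there as a target for estimating time to control from mean slopes. No section sets a pass or fail rule for a village, and microfilaremia is measured directly as well. All of that stands, and it limits the point to the stated sizing rationale.

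It is also fair that the planned 400 exceeds the one-sided exact minimum of 386. With a one-sided test, a true rate of 0.5% and no clustering, the design as planned does reach 80%. What fails is the quoted 335, and both sizes under the two-tailed alpha of Section 7.2.

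Four stronger readings are tempting, but the documents do not support them:

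- That realistic power is 15% to 43%. This needs true rates of 1.0% to 1.5%, which no section gives, together with n = 400 and a one-sided test.
- That antigenemia of 0.5% means microfilaremia of about 0.125%. Section 4 pairs two thresholds; it gives no proportional relation below them.
- That a village exactly at 2% passing only 4% of the time is a fault. At a true 2% the claim is false, and 4% is the type I error working as intended.
- That failure to show antigenemia below 2% will be read as failure of MDA. No section says so.

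That the 0.5% was carried over from microfilaremia is likewise an inference, though the documents offer no other rate.

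**Conclusion.** The point holds as a stated power that the stated size does not have. The 80% is given without the true rate it needs. At the only rate available, the shortfall at 335 is 4 percentage points one-sided (76%) and 30 points two-tailed (50%). At 400, power is 86% or 68%. If true antigenemia were 1.0% to 1.5%, per-village power would lie between 4% and 43% across both sizes and both tests. That range rests on assumed rates; persistence of antigen makes them plausible, not established. All figures are exact binomial against 2%, before clustering. The comparison of annual with twice-yearly MDA is not put in doubt.

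**What to change.** In Sections 4 and 7.2:

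- Remove the unconditional 80% power and the 335 minimum for antigenemia.
- State the assumed true antigenemia rate, the sidedness and the method.
- Say that at a true 0.5% the exact minimum is 386 (one-sided .05) or 436 (.025 per tail), each being the first n to reach 80%, before clustering.
- Print power for the planned 400 at 0.5%, 1% and 1.5%.
- Report village antigenemia rates with confidence intervals, as descriptive results.

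Optionally, add a cluster-adjusted estimate for each treatment zone from the roughly 1,600 people already planned. The text should then show power at both 1% and 1.5% from Step 5, not only the favourable one. It should say that the design effect of 1.5 is an assumption and that a zone figure can hide a village above 2%.

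The cost is revised wording and one short table, plus one extra estimate if the zone option is taken. The stated per-village power becomes less favourable. No added enrolment is needed, and the primary analysis stays as it is.

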The antigenemia prevalence is expressed as filarial antigenemia rate (proportion of examined individuals with filarial parasite antigenemia detected with the Binax Now Filariasis Card Test). To estimate the effect of MDA on antigenemia prevalence, we will tabulate mean rates of antigenemia across the four sentinel sites from each treatment zone (annual vs. twice annual MDA) over years of observation including the baseline. A generalized linear mixed model (GLMM) **with a logistic link function** will be used to account for the correlation of observations clustered within the same household from the same sentinel site. The model to estimate the difference in the odds of antigenemia includes treatment regimen and year of observation, and interaction between treatment regimen and year of observation. Some covariates that will be adjusted for in the analysis include sentinel sites, history of lymphedema, scrotal swelling (hydrocele) and prior treatment for LF as well as demographic variables of interest. Modeling will be performed with use of PROC GLIMMIX in SAS 9.2. CONTRAST statements will be used to test the significance of the log odds of antigenemia between the two treatment regimens at each year of observation. The difference of slope of rate decrease between the two regimens over the years of observations will also be tested with CONTRAST statements in PROC GLIMMIX. The resulting estimates will be converted to odds ratios with 95% confidence interval calculated from the robust estimator of variance. The other binary outcome variables (microfilaremia and anti-filarial antibody) will be analyzed with the same technique.

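### The per-village minimum of 335, with its stated 95% confidence and 80% power, makes no allowance for taking 4 to 5 people from each household; the planned 400 absorbs only a small household correlation

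*Combined protocol and SAP*

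**What the plan says.** Section 4 sets the sample for each village by "sampling approximately 100 randomly selected households per sentinel site (village) to produce N of 400", and adds "We expect to collect 4 to 5 blood samples per household". The household is therefore the unit drawn and the person is the unit tested.

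For antigenemia, section 4 says "The target number of samples per village is close to the minimum sample size of 335", the number "needed to show that the rate of antigenemia (card test) positivity is less than 2% (with 95% confidence and 80% power". For *B. timori* it repeats 335 as the number "needed to show that the MF rate is less than 2% (with 95% confidence and 80% power, assuming an actual rate of 0.5" per cent.

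Section 7.2 states that, unless otherwise noted, "all sample sizes in this protocol were calculated using a binomial power calculator", with alpha 0.05, two-tailed tests and power 0.80. It gives no ICC or design effect. It refers to robustness contingencies in an appendix, but the appendix text available holds only laboratory and field procedures.

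Section 7.3 describes the surveys as cluster surveys. Section 7.4 fits a mixed model to "account for the correlation of observations clustered within the same household from the same sentinel site".

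**The concern.** The analysis plan treats people in one household as correlated, while the sample-size statement treats them as independent. If infection aggregates in households, 400 people from 100 households carry less information about a village's prevalence than 400 people drawn singly. A binomial confidence or power figure is then too favourable.

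Below 2% antigenemia is a control target in section 7.4, and section 4 links it to the microfilaremia elimination target. Overstated confidence errs towards describing a village as below target when it is not. The problem concerns the missing clustering allowance, so it would remain with any binomial minimum, whatever its value.

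**Working it through.** **Inputs.** From section 4: limit 2%, assumed true rate 0.5% (stated in the *B. timori* paragraph only), minimum 335, planned 400 from about 100 households, m = 4 to 5 per household. From section 7.2: binomial method, alpha 0.05, power 0.80. The household ICC is not in the documents; 0 to 0.3 is assumed here to show a range. Village population sizes are not given, so no finite-population correction is applied.

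**1. Reproduce 335.** Take an exact binomial test for independent people, one-sided 5%, with null 0.5%, alternative 2% and rejection at 5 or more positives.
- n = 335: P(X ≥ 5 | 0.5%) = 0.0277; P(X ≥ 5 | 2%) = 0.8007.
- n = 334: power 0.7986.

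So 335 is the smallest size reaching 80%, and it has a design effect of exactly 1. It is reproduced only one-sided and only with 0.5% as the null. The same test two-sided needs 394. With 2% as the null it needs 386 one-sided, and 335 gives 76% power. These are separate matters, but they mean that a restatement must name the null.

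**2. Power at 335 with clustering.** Households are modelled as beta-binomial and their totals convolved exactly, with 67 households of 5 and the same cut-off. Power is 80.1%, 77.5%, 75.2% and 71.5% at ICC 0, 0.05, 0.10 and 0.20. The margin at ICC 0 is only 0.07 percentage points, so practically any positive ICC takes power below 80%.

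**3. What the planned 400 covers.** D = 1 + (m − 1) × ICC; effective N = 400 / D; needed N = 335 × D.

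| ICC | m = 4: D | effective N | needed N | m = 5: D | effective N | needed N |
|---|---|---|---|---|---|---|
| 0.05 | 1.15 | 348 | 386 | 1.20 | 333 | 402 |
| 0.10 | 1.30 | 308 | 436 | 1.40 | 286 | 469 |
| 0.20 | 1.60 | 250 | 536 | 1.80 | 222 | 603 |
| 0.30 | 1.90 | 211 | 637 | 2.20 | 182 | 737 |

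Break-even is D = 400 / 335 = 1.19. This gives ICC = 0.194 / 3 = 0.065 with 4 per household, or 0.194 / 4 = 0.049 with 5.

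**4. Error against a 2% null at 400.** The largest count with P(X ≤ c | 400, 2%) at or below 5% is c = 3. This rule is derived here and is not stated in the plan. The chance of 3 or fewer positives at a true 2% is:

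| ICC | 100 × 4 | 80 × 5 |
|---|---|---|
| 0 | 4.1% | 4.1% |
| 0.05 | 5.2% | 5.6% |
| 0.10 | 6.3% | 7.1% |
| 0.20 | 8.7% | 10.1% |
| 0.30 | 11.0% | 13.1% |

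The error crosses 5% at an ICC of about 0.04 (100 × 4) or 0.03 (80 × 5).

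**5. The other direction at 400.** With 0.5% as the null (100 × 4, 6 or more positives), alpha is 1.6%, 2.4%, 3.2% and 4.6% at ICC 0, 0.05, 0.10 and 0.20. Power is 81.2%, 79.2%, 77.5% and 74.5%. The 5% level holds over this range, and the loss shows up in power.

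**The case against.** The strongest reply is that 400 exceeds 335 by 19%, that no ICC is given, and that 95% confidence is kept at low ICC: with 100 × 4 the error against 2% is 4.7% at ICC 0.03 and 4.96% at 0.04. This stands. A reader might infer that the stated confidence is simply not delivered; the documents do not support that, because it depends on an unknown ICC. On the other side, section 4 does not describe the excess over 335 as a clustering allowance.

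Second, the plan has no per-village pass/fail rule. Section 7.4 estimates time to target from mean slopes and compares regimens with a mixed model that includes household correlation. This also stands. Neither study hypothesis rests on declaring a single village below 2%, and a reader should not conclude that the regimen comparison is undermined. The mixed model does not, however, supply a clustered limit for the per-village claim in section 4.

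Third, a reader might quote a fall in power from 86% to 68% when the error is held at or below 5% at 400. Most of that is discreteness, as the cut-off steps from 3 to 2. Held at exactly 5% by a randomised test (100 × 4), power is 87%, 84%, 78% and 71% at ICC 0, 0.05, 0.10 and 0.20.

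Fourth, 100 households of 5 would give 500 people. Then D up to 500 / 335 = 1.49 is covered, an ICC of 0.49 / 4 = 0.12. A small village would also offset part of the loss.

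Last, section 7.2 refers to contingencies in an appendix. The available text does not contain them, so they neither confirm nor rebut an allowance.

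**Conclusion.** The point holds in a limited form. The 335 and its stated confidence and power assume independent people, as the exact reproduction shows, although the design samples households and the analysis plan accepts the correlation. At 335 the 80% power is lost with practically any positive household ICC. At 400 the stated properties are not assured. The margin covers an ICC of up to 0.049–0.065 by the design-effect calculation, and the error against a 2% null exceeds 5% from an ICC of about 0.03–0.04. The excess is modest at ICC 0.1 (error 6–7%) and about double the nominal level at ICC 0.2 (9–10%).

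These sizes rest on an assumed ICC range, equal household sizes, a beta-binomial model and no finite-population correction. The consequence is confined to the section 4 claim and to any per-village statement of being below 2%.

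**What to change.** Keep about 400 per village. In section 4, for both antigenemia and *B. timori* microfilaremia:
- restate the confidence and power with a design effect of 1 + (m − 1) × ICC, for m of 4 and 5 and a stated ICC range;
- say which rate is the null and whether the test is one- or two-sided;
- if the excess of 400 over 335 is meant as a clustering allowance, say so and give the ICC that it covers.

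In section 7.4, base any per-village statement of being below 2% on an upper confidence limit that allows for household clustering, from a beta-binomial model or a bootstrap that resamples households.

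The cost is protocol wording and a small addition to the analysis, with no extra participants. The downside is that the stated power or confidence becomes slightly less favourable.
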